##### 5.2.1.3 Further safety endpoints

#### 5.2.1.3.2 Further criteria of interest

Safety and tolerability of the investigational drugs will be assessed based on:

- AEs (including clinically relevant findings from physical examination)
- Safety laboratory tests
- 12-lead single ECGs or Holter ECG recordings
- Vital signs (blood pressure, pulse rate)

### 5.2.2 Assessment of adverse events

#### 5.2.2.1 Definitions of adverse events

##### **Adverse event**

An adverse event (AE) is defined as any untoward medical occurrence in a patient or clinical investigation subject administered a medicinal product and which does not necessarily have to have a causal relationship with this treatment.

An AE can therefore be any unfavourable and unintended sign (including an abnormal laboratory finding), symptom, or disease temporally associated with the use of a medicinal product, whether or not considered related to the medicinal product.

The following should also be recorded as an AE in the CRF and BI SAE form (if applicable):

- Worsening of the underlying disease or of other pre-existing conditions
- Changes in vital signs, ECG, physical examination, and laboratory test results, if they are judged clinically relevant by the investigator

If such abnormalities already exist prior to trial inclusion, they will be considered as baseline conditions and should be collected in the eCRF only.

### **Serious adverse event**

A serious adverse event (SAE) is defined as any AE which fulfils at least one of the following criteria:

- results in death
- is life-threatening, which refers to an event in which the patient was at risk of death at the time of the event; it does not refer to an event that hypothetically might have caused death if more severe
- requires inpatient hospitalisation
- requires prolongation of existing hospitalisation
- results in persistent or significant disability or incapacity
- is a congenital anomaly/birth defect
- is deemed serious for any other reason if it is an important medical event when based upon appropriate medical judgment which may jeopardise the patient and may require medical or surgical intervention to prevent one of the other outcomes listed in the above definitions. Examples of such events are intensive treatment in an emergency room or at home for allergic bronchospasm, blood dyscrasias or convulsions that do not result in hospitalisation or development of dependency or abuse.

### **AEs considered ‘Always Serious’**

Cancers of new histology and exacerbations of existing cancer must be classified as a serious event regardless of the time since discontinuation of the drug and must be reported as described in [5.2.2.2](#), subsections “AE Collection” and “AE reporting to sponsor and timelines”.

In accordance with the European Medicines Agency initiative on Important Medical Events, Boehringer Ingelheim has set up a list of further AEs, which, by their nature, can always be considered to be ‘serious’ even though they may not have met the criteria of an SAE as defined above.

The latest list of ‘Always Serious AEs’ can be found in the eDC system, an electronic data capture system which allows the entry of trial data at the trial site. These events should always be reported as SAEs as described above.

### **Adverse events of special interest**

The term adverse events of special interest (AESI) relates to any specific AE that has been identified at the project level as being of particular concern for prospective safety monitoring and safety assessment within this trial, e.g. the potential for AEs based on knowledge from other compounds in the same class. AESIs need to be reported to the sponsor’s Pharmacovigilance Department within the same timeframe that applies to SAEs, please see Section 5.2.2.2.

The following is considered as AESI:

Proprietary confidential information © 2019 Boehringer Ingelheim International GmbH or one or more of its affiliated companies

### Hepatic injury

A hepatic injury is defined by the following alterations of hepatic laboratory parameters:

- an elevation of AST (aspartate transaminase) and/or ALT (alanine transaminase)  $\geq 3$ -fold ULN combined with an elevation of total bilirubin  $\geq 2$ -fold ULN measured in the same blood sample, or
- aminotransferase (ALT, and/or AST) elevations  $\geq 10$  fold ULN

These lab findings constitute a hepatic injury alert and the subjects showing these lab abnormalities need to be followed up according to the 'DILI checklist' provided in the ISF. In case of clinical symptoms of hepatic injury (icterus, unexplained encephalopathy, unexplained coagulopathy, right upper quadrant abdominal pain, etc.) without lab results (ALT, AST, total bilirubin) available, the Investigator should make sure that these parameters are analysed, if necessary in an unscheduled blood test. Should the results meet the criteria of hepatic injury alert, the procedures described in the DILI checklist should be followed.

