4. End-of-trial examination includes physical examination, vital signs, ECG, safety laboratory, pregnancy test in women, recording of AEs and concomitant therapies
5. Only urine drug screening, alcohol breath test, and pregnancy test in women will be done at this time point.
6. AEs and concomitant therapies will be recorded throughout the trial, but will be specifically asked for at the time points indicated in the [Flow Chart](#) above.
7. Holter ECG (◀—|—|→). The arrows refer to start (►) and end (◀) of Holter ECG recording. The sign | indicates that trigger points will be set at the Holter device for extraction of triplicate 12-lead 10 second ECGs. The time is an approximate. For acceptable time deviations please refer to Section [6.1](#). The sign \* indicates that a trigger point will be set at the Holter device at the time point of drug administration.
8. Single 12-lead ECG for clinical evaluation by the investigator only
9. No BI 409306 PK samples after open-label moxifloxacin administration

Proprietary confidential information © 2019 Boehringer Ingelheim International GmbH or one or more of its affiliated companies

10. 12-lead Holter ECG is performed at Visit 2 and will be used for extraction of 7 drug-free 10-second run-in ECGs (over at least 8 hours as shown in [Flow Chart \(B\)](#)) and for analyses of arrhythmic events (at least 24 h recording as shown in Flow Chart (B)). The start of Holter ECG recording on Day -7 to -4 can be no earlier than 1 day after screening.
11. 12-lead Holter ECG recording on Day 1 and 2; recording to be stopped no earlier than 24 h after drug administration
12. Admission to the trial site should not be later than 10 hours prior to drug administration
13. Letters A, B, C and D describe different sets of safety laboratory examinations (see Table [5.2.3: 1](#))
14. in Visit 2 only

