### **3.3.4 Removal of subjects from therapy or assessments**

#### **3.3.4.1 Removal of individual subjects**

An individual subject is to be removed from the trial:

1. If the subject withdraws consent for trial treatment or trial participation, without the need to justify the decision
2. If the subject needs to take concomitant drugs that interfere with the investigational product or other trial medication
3. If the subject is no longer able to participate for other medical reasons (such as pregnancy, surgery, AEs, or diseases)
4. If the subject shows an elevation of AST and/or ALT  $\geq 3$ -fold ULN combined with an elevation of total bilirubin  $\geq 2$ -fold ULN (measured in the same blood sample) and/or needs to be followed up according to the 'DILI checklist' provided in the ISF.
5. If the subject shows an elevation of AST and/or ALT  $\geq 3$ -fold ULN.
6. In case of relevant individual QT prolongations in safety ECG recordings, i.e. absolute QT or QTc  $> 500$  msec and/or QTc increase  $> 60$  msec from baseline (i.e., pre-dose), as confirmed by a repeat ECG recording.
7. In case of a serious adverse reaction, or in case of a severe non-serious adverse reaction not listed in Table 7.6: 1 of the current Investigator's brochure.

Proprietary confidential information © 2019 Boehringer Ingelheim International GmbH or one or more of its affiliated companies

In addition to these criteria, the investigator may discontinue subjects at any time based on his or her clinical judgement.

A subject can also be removed from the trial if eligibility criteria are being violated or if the subject fails to comply with the protocol (for instance, by non-adherence to dietary rules, or non-attendance at study assessments).

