If a subject is removed from or withdraws from the trial prior to first administration of trial medication, the data of this subject will not be entered in the case report form (CRF) or trial database and will not be reported in the clinical trial report (CTR). If a subject is removed from or withdraws from the trial after first administration of trial medication, this will be documented and the reason for discontinuation must be recorded in the CRF. In this case, the data will be included in the CRF/trial database and will be reported in the CTR. At the time of discontinuation a complete end-of-trial examination will be performed if possible and the information will be recorded in the CRFs. If the discontinuation occurs before the end of the REP (see Section [1.2](#)), the discontinued subject should if possible be questioned for AEs and concomitant therapies at or after the end of the REP in order to ascertain collection of AEs and concomitant therapies throughout the REP, if not contrary to any consent withdrawal of the subject. These discontinuations will be discussed in the CTR.

If it is known that a subject becomes pregnant during the trial, administration of the trial medication has to be stopped immediately, and the subject has to be removed from the trial. The subject is to be followed until she has given birth or until the end of pregnancy. The subject's data are to be collected until the end of the trial (last visit of last subject) and reported in the clinical trial report. For reporting of pregnancy and events refer to Section [5.2.2.2](#).

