### **5.2.3 Assessment of safety laboratory parameters**

For the assessment of laboratory parameters, blood and urine samples will be collected by the trial site at the time points indicated in the [Flow Chart](#) after the subjects have fasted for at least 10 h. Over-night fasting is not required for drug screening and pregnancy test at admission and at the discretion of the investigator or designee for re-tests.

The parameters that will be determined are listed in Tables [5.2.3: 1](#) and [5.2.3: 2](#). Reference ranges will be provided in the ISF, Section [10](#).

Manual differential white blood cell count or urine sediment examinations will only be performed if there is an abnormality in the automatic blood cell count or in the urinalysis, respectively.

Proprietary confidential information © 2019 Boehringer Ingelheim International GmbH or one or more of its affiliated companies

Table 5.2.3: 1

Routine laboratory tests

Functional lab group	BI test name [comment/abbreviation]	A	B	C	D
Haematology	Haematocrit Haemoglobin Red Blood Cell Count/Erythrocytes White Blood Cells/Leucocytes Platelet Count/Thrombocytes (quant)	X X X X X	-- -- -- -- --	-- -- -- -- --	X X X X X
Automatic WBC differential, relative	Neutrophils/Leukocytes; Eosinophils/Leukocytes; Basophils/Leukocytes; Monocytes/Leukocytes; Lymphocytes/Leukocytes	X	--	--	X
Automatic WBC differential, absolute	Neutrophil, absol.; Eosinophils, absol.; Basophils, absol.; Monocytes, absol.; Lymphocytes, absol.	X	--	--	X
Manual differential WBC (if automatic differential WBC is abnormal)	Neut. Poly (segs); Neut. Poly (segs), absol.; Neutrophils Bands; Neutrophils Bands, absol.; Eosinophils/Leukocytes; Eosinophils, absol.; Basophils/ Leukocytes; Basophils, absol.; Monocytes/ Leukocytes; Monocytes, absol.; Lymphocytes/Leukocytes; Lymphocytes, absol.				
Coagulation	Activated Partial Thromboplastin Time Prothrombin time Prothrombin time – INR (International Normalization Ratio)	X X X	-- -- --	-- -- --	X X X
Enzymes	AST (Aspartate transaminase) /GOT, SGOT ALT (Alanine transaminase) /GPT, SGPT Alkaline Phosphatase Gamma-Glutamyl-Transferase Amylase Lipase	X X X X X X	-- -- -- -- -- --	X X -- X -- --	X X X X X X
Hormones	Thyroid Stimulating Hormone	X	--	--	--
Substrates	Glucose (Plasma) Creatinine Bilirubin, Total Bilirubin, Direct Protein, Total C-Reactive Protein (Quant) Cholesterol, total Triglyceride	X X X X X X X	-- -- -- -- -- -- --	-- -- -- -- -- -- --	X X X X X X X

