#### A: Parameters to be determined at Visit 1 (screening examination)

B: Parameters to be determined prior to dosing and at 2:00 PTM on Day 1 of Visits 2 to 6

C: Parameters to be determined on prior to discharge on Day 2 of Visits 2 to 6

D: Parameters to be determined at Visit 7 (end-of-trial examination)

The tests listed in Table 5.2.3: 2 are exclusionary laboratory tests which may be repeated as required. The results will not be entered in the CRF/database and will not be reported in the CTR. Except for pregnancy test and drug screening, it is planned to perform these tests during screening only. Pregnancy testing in women will be performed at screening, prior to each treatment period (on Days -1 or 1), and as part of the end-of-trial examination. Drug screening will be performed at screening and prior to each treatment period (on Days -1 or 1).

Table 5.2.3: 2 Exclusionary laboratory tests

Functional lab group	Test name
Drug screening (urine)	Amphetamine/MDA Barbiturates Benzodiazepine Cannabis Cocaine Methadone Methamphetamines/MDMA/XTC Opiates Phencyclidine Tricyclic antidepressants
Infectious serology (blood)	Hepatitis B surface antigen (qual) Hepatitis B core antibody (qual) Hepatitis C antibodies (qual) HIV-1 and HIV-2 antibody (qual)
Pregnancy test (urine)	Beta human chorionic gonadotropin (beta-HCG)

To encourage compliance with alcoholic restrictions, a breath alcohol test (Alcotest® 7410, Dräger AG, Lübeck, Germany) will be performed prior to each treatment period (on Days -1

Proprietary confidential information © 2019 Boehringer Ingelheim International GmbH or one or more of its affiliated companies

or 1), and may be repeated at any time during the study at the discretion of an investigator or designee. The results will not be included in the CTR.

The laboratory tests listed in Table [5.2.3: 1](#) and [5.2.3: 2](#) will be performed at with the exception of the drug screening and pregnancy tests. These tests will be performed at the trial site using M-10/14-PDT test and HCG-K20 test, respectively, or comparable test kits.

Laboratory data will be transmitted electronically from the laboratory to the trial site.

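### The Day 2 blood sample has AST and ALT but no total bilirubin, so an asymptomatic AST/ALT of 3x to <10x ULN cannot be classified for the hepatic-injury AESI on that sample

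*Protocol*

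**What the plan says.** Protocol 5.2.2.1 (Hepatic injury) defines the AESI by two limbs. Limb 1 is AST and/or ALT of at least 3x ULN with total bilirubin of at least 2x "ULN measured in the same blood sample". Limb 2 is AST and/or ALT of at least 10x ULN, with no bilirubin condition. SAP 7.8.1 repeats both limbs. The laboratory part of removal criterion 4 (Protocol 3.3.4.1) uses the limb 1 pairing.

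The laboratory schedule is in Protocol 5.2.3. Set C is defined as "C: Parameters to be determined on prior to discharge on Day 2 of Visits 2 to 6". Table 5.2.3: 1 marks AST, ALT and GGT in column C and nothing else.

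Three other rules bear on the point:

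- Section 5.2.2.1 tells the investigator to obtain missing liver tests, but the instruction opens "In case of clinical symptoms of hepatic injury". It also states that "the subjects showing these lab abnormalities need to be followed up according to the" DILI checklist; that is, the checklist follows once the alert values are present.
- Removal criterion 5 acts on transaminases alone: "If the subject shows an elevation of AST and/or ALT" of at least 3x ULN, the subject is removed.
- For a removed subject, Section 3.3.4.1 says: "At the time of discontinuation a complete end-of-trial examination will be performed if possible". Under Flow Chart (A), footnote 4, that examination includes the safety laboratory.

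**The concern.** The sample taken in every treatment period to look for transaminase rises leaves out the one analyte that limb 1 pairs with them. Set C consists only of liver tests, so liver surveillance is its evident purpose, and Protocol 2.3 (Safety measures) says the trial needs liver laboratory changes to be detected in good time.

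If a subject had a raised bilirubin alongside a Day 2 transaminase of 3x to <10x ULN, the event could be recognised late. It could be missed altogether if bilirubin had fallen by the next draw that measures both. An AESI must reach the sponsor within 24 hours (Protocol 5.2.2.2), and AESIs have their own table (SAP 7.8.1); both depend on the classification being made.

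**Working it through.** The plan gives no figure to reproduce. The check sets the schedule against the definition.

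**1. What each set contains (Table 5.2.3: 1 and its key)**

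| Set | When | AST, ALT | Total bilirubin |
|---|---|---|---|
| A | Screening | yes | yes |
| B | Pre-dose and 2 h, Day 1, Visits 2–6 | no (electrolytes only) | no |
| C | Day 2, Visits 2–6 | yes (plus GGT) | no |
| D | Visit 7, end of trial | yes | yes |

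The Substrates row, which holds bilirubin ("Creatinine Bilirubin, Total Bilirubin, Direct Protein, Total C-Reactive Protein (Quant"), shows eight test names against seven marks per column in the text available. Every mark in column C is a dash, so the alignment cannot change the reading.

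**2. What a set C sample can decide**

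| Day 2 AST/ALT | Limb 1 | Limb 2 | AESI status on that sample |
|---|---|---|---|
| <3x ULN | ruled out | not met | not an AESI |
| 3x to <10x ULN | needs bilirubin | not met | undetermined |
| ≥10x ULN | not needed | met | AESI |

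**3. How many samples have the gap**

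Scheduled post-dose samples with AST/ALT for a completing subject: 5 (set C) + 1 (set D) = 6. Samples that can be tested on both limbs: 1 of 6. Planned Day 2 samples: 45 × 5 = 225. Only those falling in the 3x to <10x band are affected.

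**4. How often this might happen**

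The documents give no rate for that band and none for BI 409306. The only frequencies are those for moxifloxacin used as an antibiotic (Protocol 2.3). Applying them to a single dose in healthy subjects is an assumption.

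- Transaminase increase of any size: common (≥1%) and under the 3% ceiling stated there. 45 × 0.01 = 0.45; 45 × 0.03 = 1.35. So 0.45 to <1.35 subjects.
- Increased bilirubin: uncommon (0.1% to <1%). 45 × 0.001 = 0.045; 45 × 0.01 = 0.45. So 0.045 to <0.45 subjects.

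These figures concern the 45 moxifloxacin-period samples. For the other 225 − 45 = 180, on BI 409306 or placebo, nothing is available. Within the moxifloxacin period they are upper bounds under the assumption, because the 3x to <10x band is a subset of all increases. The joint rate with bilirubin is not given.

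**5. Delay to a paired draw**

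If the next draw with both analytes falls in the end-of-trial window (Day 5 to 12, Flow Chart (A)): 5 − 2 = 3 days to 12 − 2 = 10 days after the Day 2 sample. This applies mainly to the last period. A subject removed earlier should be examined at discontinuation, so the delay would be shorter, or there would be no paired draw if the examination was not possible.

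**6. Whether another rule closes the gap**

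- The unscheduled-test instruction is triggered by symptoms.
- As worded in the protocol, the checklist applies to subjects who already show the alert values.
- Re-tests (5.2.3) and follow-up of abnormal values (6.2.4) rest on the investigator's judgement and do not name bilirubin.
- The discontinuation examination yields set D, but from a later sample.

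None of these requires bilirubin on the Day 2 blood of a subject without symptoms.

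**The case against.** The protocol already acts on this case without bilirubin. Criterion 5, added in Amendment 2 at the request of the competent authority and ethics committee, removes anyone at 3x ULN or above, and set C supplies what that rule needs. Removal then leads to an end-of-trial examination in which AST, ALT and bilirubin are measured together. Section 6.2.4 adds that subjects who stop early should have that visit, without the qualifier found in 3.3.4.1. A value that forces removal is also likely to be judged clinically relevant and followed up. The DILI checklist is held in the investigator site file and may cover an isolated rise to 3x ULN. On this view only a reporting label is left, and measuring bilirubin only at screening and end of trial, with a bilirubin-independent stop in between, is a defensible choice for single doses in healthy subjects.

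Much of this stands. There is no re-dosing risk, the chance of missing a case entirely is reduced, and the frequency is low and largely unknown. The 3-to-10-day delay is not typical of removals in periods 1 to 4. No document shows how quickly bilirubin would fall, so a missed case is a possibility, not a demonstrated outcome. The checklist's content cannot be judged from here.

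It does not remove the gap. Each safeguard gives either a later sample or a general intention. None gives the same-sample bilirubin that limb 1 asks for.

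**Conclusion.** The concern holds. On a Day 2 sample with AST or ALT of 3x to <10x ULN and no symptoms, limb 1 of the AESI and the laboratory part of removal criterion 4 cannot be determined, and the visible text does not require bilirubin to be added.

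The effect is confined to safety ascertainment: the timing and completeness of AESI classification, its expedited report and its table. Dosing decisions and the QTcF and heart-rate results are unaffected. The size in subjects cannot be estimated from the documents.

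The conclusion rests on the table as read above and on the protocol's wording of when the checklist applies. If the checklist itself requires bilirubin for an isolated rise to 3x ULN, the practical gap would narrow or close. This is a low-cost improvement that should be made; it does not threaten the trial.

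**What to change.** Either of two changes is enough:

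- Mark total bilirubin in column C of Table 5.2.3: 1.
- Add a sentence to Section 5.2.2.1 and a footnote to the table: if AST and/or ALT on Day 2 is 3x ULN or more, total bilirubin is measured in the same blood sample.

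The thresholds stay as they are. With the first option, the scheduled post-dose samples that can be classified under both limbs rise from 1 of 6 to 6 of 6. The second gives the same classification by testing only the samples that need it.

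The cost is one analyte on blood already drawn, with no extra venipuncture, and one table cell or sentence in an amendment. The downside is a small laboratory charge and occasional incidental bilirubin findings, most of which the reflex option avoids.

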### Intensity (severity) of AEs

The intensity (severity) of the AE should be judged based on the following:

Mild: Awareness of sign(s) or symptom(s) that is/are easily tolerated

Moderate: Sufficient discomfort to cause interference with usual activity

Severe: Incapacitating or causing inability to work or to perform usual activities

### Causal relationship of AEs

Medical judgment should be used to determine the relationship, considering all relevant factors, including pattern of reaction, temporal relationship, de-challenge or re-challenge, confounding factors such as concomitant medication, concomitant diseases and relevant history.

Arguments that may suggest that there is a reasonable possibility of a causal relationship could be:

- The event is consistent with the known pharmacology of the drug
- The event is known to be caused by or attributed to the drug class
- A plausible time to onset of the event relative to the time of drug exposure
- Evidence that the event is reproducible when the drug is re-introduced
- No medically sound alternative aetiologies that could explain the event (e.g. pre-existing or concomitant diseases, or co-medications)
- The event is typically drug-related and infrequent in the general population not exposed to drugs (e.g. Stevens-Johnson syndrome)
- An indication of dose-response (i.e. greater effect size if the dose is increased, smaller effect size if dose is reduced)

Arguments that may suggest that there is no reasonable possibility of a causal relationship could be:

Proprietary confidential information © 2019 Boehringer Ingelheim International GmbH or one or more of its affiliated companies

- No plausible time to onset of the event relative to the time of drug exposure is evident (e.g. pre-treatment cases, diagnosis of cancer or chronic disease within days / weeks of drug administration; an allergic reaction weeks after discontinuation of the drug concerned)
- Continuation of the event despite the withdrawal of the medication, taking into account the pharmacological properties of the compound (e.g. after 5 half-lives). Of note, this criterion may not be applicable to events whose time course is prolonged despite removing the original trigger
- Additional arguments amongst those stated before, like alternative explanation (e.g. situations where other drugs or underlying diseases appear to provide a more likely explanation for the observed event than the drug concerned)
- Disappearance of the event even though the study drug treatment continues or remains unchanged

